### Sub-study 1: Acceptability

The primary and secondary outcomes for the acceptability study and their definitions are listed in Table 2.

*Table 2. Primary and secondary acceptability outcomes*

Outcome type	Outcome definition
Primary	Observed dose intake/ consumed (g) after one week trial
Secondary	Adaptation effect (difference between observed dose intakes on first day and after one week trial)
Secondary	Reason for ending test dose (refusing the product)
Secondary	Proportion of empty sachets returned relative to the number of sachets received one week before (adherence indicator)
Secondary	Caregiver-reported product sharing (binary adherence indicator)
Secondary	Caregiver-reported number of times per day the product was consumed at home (intake frequency)
Secondary	Perceived liking scores (by caretakers) according to Likert scale
Secondary	Product ranking/selection (by mothers)

Secondary	Food frequency changes during each product trial
Secondary	Breastfeeding frequency during each product trial
Secondary	Caregiver-reported presence of an adverse effect (diarrhea, vomiting...)

### Sub-study 2: Microbiome and gut health

The primary outcome of this study is species richness, measured through shotgun metagenomics. Secondary outcomes include inflammation markers, enteropathogen burden, and microbiome composition. Inflammation markers ( $\alpha$ -1 antitrypsin, lipocalin-2, fecal neopterin, myeloperoxidase) will be analyzed via enzyme-linked immunosorbent assay (ELISA) kits. Enteropathogen burden and microbiome composition will be assessed using TaqMan Array Card assays and shotgun metagenomics, respectively.

### Sub-study 3: Costing

Outcomes for the costing study are listed in Table 3.

*Table 3. Costing outcomes and their definitions*

Outcome	Category	Definition
Cost per MAM child admitted into treatment	Cost-efficiency	Total cost of MAM treatment divided by the number of MAM children admitted into treatment during that time period
Cost per SAM child admitted into treatment	Cost-efficiency	Total cost of SAM treatment divided by the number of SAM children admitted into treatment during that time period
Cost per treated MAM child recovered	Cost-effectiveness	Total cost of MAM treatment divided by the number of MAM children recovered during that period
Cost per treated SAM child recovered	Cost-effectiveness	Total cost of SAM treatment divided by the number of SAM children recovered during that period

### Sample size and statistical power

#### Main trial

We estimate a total sample size of 1080 children with SAM (360 per arm) and 1080 children with MAM (360 per arm) will provide sufficient statistical power to demonstrate non-inferiority for each comparison, with a non-inferiority margin of relative 12.5%, assuming a recovery rate in the control of 76% and a loss to follow up of 15% (Table 4). The sample size will be smaller for analyses of relapse, because only recovered children will be included in the analysis. All calculations assume a one-sided  $\alpha = 0.05$  for non-inferiority and two-sided  $\alpha = 0.05$  for superiority analyses,  $\beta = 0.8$ , and 15% attrition. While the key objectives of this research are to evaluate effects of the alternative RUTFs on recovery and relapse, we consider as primary outcomes any outcome for which we have adequate power for clinically or policy meaningful effect sizes (5).

 Stata commands `ssi` for continuous outcomes and `artbin` for binary outcomes were used for non-inferiority analyses, and `power twomeans` for continuous outcomes and `power twoproportions` for binary outcomes were used for superiority analyses. Outcome proportions, means, or standard deviations were taken from relevant studies in literature as delineated in Table 4.

Table 4. Calculations of detectable effect sizes for all outcomes

Outcome	Outcome prevalence in the literature	Type of analysis	Non-inferiority margin (relative) with $\geq 80\%$ power (Non-inferiority)	Detectable effect size at 80% power (Superiority)	Rank of outcome
Anthropometric recovery at discharge	MAM recovery (with RUSF*): 73% (6); 73% (7); 85% (8)  SAM recovery: 55.4% (9); 82.3% (10); 76% (11); 71% (pooled estimate from meta-analysis) (12)	Non-inferiority	12.5% relative margin		Primary
Relapse to wasting within 3-months post-discharge	Post-MAM relapse: 30% within 3 months (13); 33% within 12-months (14)  Post-SAM relapse: 6.8% 3-month cumulative incidence (15); 24% 2-month cumulative incidence (16); 30% within 3-months (unpublished)	Superiority		Risk difference of 11%; Relative risk = 0.72	Primary
Length of stay (LOS) among recovered children	MAM: 36.4 days (SD 50.4 days)(17); 5.9 weeks (95% CI: 4.9, 7.0)(18) SAM: 56 days (assumed 41 day SD) (9)	Non-inferiority	MAM: 4.9 days; 12.5% relative margin SAM: 8 days; 12.5% relative margin		Primary
Weight gain during treatment	MAM: 4.1 g/kg/day (SD = 3.0) (17), SAM: 3 g/kg/day (SD = 4.7) in 6-23 mo and 8.6 g/kg/day (SD = 4.7) in 24-59 mo (19)	Non-inferiority	MAM: 0.14 kg; 12.5% relative margin SAM: 0.91 g/kg/day; 12.5% relative margin		Primary
Anthropometry at discharge from treatment	MAM: All estimates from Fabiansen et al (20) WLZ: -1.52	Non-inferiority	MAM:		Primary

	
MUAC: 130.1 mm HAZ: -1.86 WAZ: -2.6 (assumed from SAM because estimates not available) Weight: 7.8 kg Height: 72.9 cm
 
SAM: All estimates from Kangas et al(9) WLZ: -1.9 MUAC: 125.9 mm HAZ: -2.3 WAZ: -2.6 Weight: 7.3 kg Height: 71.6 cm
		
WLZ: 0.2 z-scores; 12.5% relative margin MUAC: 6.8 mm; 5% relative margin HAZ: 0.2 z-scores; 12.5% relative margin WAZ: 0.4 z-scores; 12.5% relative margin Weight: 0.4 kg; 5% relative margin Height: 3.8 cm; 5% relative margin
 
SAM: WLZ: 0.3 z-scores; 12.5% relative margin MUAC: 6.3 mm; 5% relative margin HAZ: 0.3 z-scores; 12.5% relative margin WAZ: 0.4 z-scores; 12.5% relative margin Weight: 0.4 kg; 5% relative margin Height: 3.8 cm; 5% relative margin
		
Anthropometry at 3-months post-discharge	MAM: All estimates from Fabiansen et al (20)	Superiority		MAM: WLZ: 0.26	Primary

	WLZ: -1.52 MUAC: 130.1 cm HAZ: -1.86 WAZ: -2.6 (assumed from SAM because estimates not available) Weight: 7.8 kg Height: 72.9 cm  SAM: All estimates from Kangas et al(9) WLZ: -1.9 MUAC: 125.9 cm HAZ: -2.3 WAZ: -2.6 Weight: 7.3 kg Height: 71.6 cm			MUAC: 2.46 cm HAZ: 0.39 WAZ: 0.37 Weight: 0.39 kg Height: 1.87 cm  SAM: WLZ: 0.37 MUAC: 3.13 cm HAZ: 0.48 WAZ: 0.37 Weight: 0.55 kg Height: 2.76 cm	
Hemoglobin at discharge	MAM: 108 g/L (SD = 13) (21) SAM: 108.6 g/L (SD = 11.2) (22)	Non-inferiority	MAM: 2.7 g/L; 2.5% relative margin SAM: 2.2 g/L; 2.5% relative margin		Primary
Hemoglobin at 3-months post-discharge	MAM: 108.0 g/L (SD = 13) (21) SAM: 108.6 g/L (SD = 11.2) (22)	Superiority	--	MAM = 2.9 g/L SAM = 2.9 g/L	Primary
Default from treatment	MAM: 6.8% (17) SAM: 8.5% (9)	Non-inferiority	MAM: 50% relative margin SAM: 45% relative margin		Secondary
Transfer to inpatient treatment	MAM: 5.8% (20) SAM: 20.1% (9)	Non-inferiority	MAM: 70% relative margin SAM: 40% relative margin		Secondary
Non-response to treatment	MAM: 32.2% (18), 28%(20) SAM: 12.5% (9)	Non-inferiority	MAM: 30% relative margin SAM: 25% relative margin		Secondary

Compliance to treatment services (attendance at visits)	MAM: 87% (17) SAM: 11.1% (11)	Non-inferiority	MAM: 50% relative margin SAM: 10% relative margin		Secondary
Relapse to SAM	Note: Reporting of relapse as MAM vs SAM is not common. Daures et al reported 88.6% of relapses were MAM (23), so we apply this proportion to the below rates.  Post-MAM relapse to SAM: 30% within 3 months (13); 33% within 12-months (14)  Post-SAM relapse to SAM: 6.8% 3-month cumulative incidence (15); 24% 2-month cumulative incidence (16); 30% within 3-months (unpublished)	Superiority		MAM and SAM (Assumed to be same): RR = 0.34	Secondary
Relapse to MAM	Note: Reporting of relapse as MAM vs SAM is not common. Daures et al reported 88.6% of relapses were MAM (23), so we apply this proportion to the below rates.  Post-MAM relapse to SAM: 30% within 3 months (13); 33% within 12-months (14)  Post-SAM relapse to SAM: 6.8% 3-month cumulative incidence (15); 24% 2-month cumulative incidence (16); 30% within 3-months (unpublished)	Superiority	-	MAM and SAM (Assumed to be same): RR = 0.689	Secondary
Morbidity	MAM: 61.1% (any illness) (17) SAM: 60.0% (any illness) (9)	Non-inferiority	MAM: 17.5% relative margin SAM: 17.5% relative margin		Secondary

Anemia at discharge	MAM: 49% prevalence (21) SAM: 51% prevalence (22)	Non-inferiority	MAM: 17.5% relative margin SAM: 17.5% relative margin	--	Secondary
Anemia at 3-months post-discharge	MAM: 49% prevalence (21) SAM: 51% prevalence (22) *estimates are sourced from studies presenting data at discharge because post-discharge data not available	Superiority	--	MAM: 23.3% relative SAM: 24.2% relative	Secondary
Mortality		Non-inferiority			Exploratory

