We estimate a total sample size of 1080 children with SAM (360 per arm) and 1080 children with MAM (360 per arm) will provide at least 90% statistical power to demonstrate non-inferiority for each comparison, with a non-inferiority margin of 10 percentage points, assuming a recovery rate in the control of 77% (Table 4). For relapse outcomes, sample size will be smaller, and thus power will be lower, because only recovered children will be included in the analysis. All calculations assume a one-sided $\alpha = 0.05$ for non-inferiority and two-sided $\alpha = 0.05$ for superiority analyses.

Table 4. Sample size calculations

Scenarios with at least 80% power are **bolded**.

Primary outcome	Analysis type	Sample size per arm	Outcome prevalences reported in literature	Non-inferiority margin or detectable effect size	Assumption on control group outcome prevalence/means in sample size calculations	Power per comparison
Anthropometric recovery at discharge	Non-inferiority	360 MAM and 360 SAM children/arm enrolled; 306 MAM and 306 SAM children in analysis after 15% attrition	MAM recovery (with RUSF*): 73% (13); 73% (14); 85% (15) SAM recovery : 55.4% (16); 82.3% (17); 76% (18); 71% (pooled estimate from meta-analysis) (19)	10 percentage points (absolute difference)	55.4% (vs 45.4%)	85.6%
					77.0% (vs 67.0%)	90.0%
					82.3% (vs 72.3%)	96.8%
Relapse to wasting within 3-months post-discharge	Superiority	236 children/arm in analysis (assuming 77% of the 306 children recover)	Post-MAM relapse : 30% within 3 months (period prevalence) (20); 33% within 12-months (21) Post-SAM relapse : 6.8% 3-month cumulative incidence (22); 24% 2-month cumulative incidence (23); 30% within 3-months (unpublished); 2.6 episodes per child-year (unpublished); 1.3	35% relative reduction (incidence rate ratio = 0.65)	Incidence of 2.6 episodes per child-year	80.0%
					Prevalence of 30% (vs 20%)	71.0%

			episodes per child-year (unpublished)			
--	--	--	--	--	--	--

*RUSF = ready-to-use supplementary food

Study procedures

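### SAP Table 4 sizes MAM recovery on 76% and MAM non-response on 28–32.2%; together these exceed 100%, so the two rows' stated power of at least 80% rests on control rates that cannot both hold

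*SAP*

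**What the plan says.** The SAP (Sample size and statistical power, Main trial) claims adequate power in each stratum. For the MAM stratum its words are "1080 children with MAM (360 per arm) will provide sufficient statistical power to demonstrate non-inferiority for each comparison". The margin for recovery is 12.5% on the relative scale. The sizing rests on two further inputs, given as "assuming a recovery rate in the control of 76% and a loss to follow up of 15" per cent. One control recovery rate serves both strata.

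SAP Table 4 gives margins said to carry at least 80% power. Footnote 1 says that the proportions used in the calculations came from the literature values in that table. The relevant rows are:

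- Recovery: MAM 73%, 73% and 85%; SAM 55.4%, 82.3%, 76% and 71%; margin 12.5% relative.
- Non-response: "MAM: 32.2% (18), 28%(20) SAM: 12.5% (9"; margin 30% relative for MAM and 25% for SAM.
- Default: "MAM: 6.8% (17) SAM: 8.5% (9".
- Transfer to inpatient care: "MAM: 5.8% (20) SAM: 20.1% (9".

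The numbers in brackets are source references. All three SAM failure rates come from source 9, whose listed recovery is 55.4%.

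Three other places bear on this. SAP Table 1 counts failure to meet recovery criteria after 3 months as non-response, and says non-responders are referred to inpatient care. The SAP section on missing data treats default as a treatment outcome. Protocol Table 4 gives the analysed numbers, "306 MAM and 306 SAM children in analysis after 15% attrition", and for relapse "236 children/arm in analysis (assuming 77% of the 306 children recover".

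**The concern.** Recovery and non-response are alternative results of one treatment course. In MAM, Table 4 assigns them control rates that add to more than 100%, and then states at least 80% power for both.

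With a relative margin, power depends strongly on the control rate. Lowering recovery to make room for non-response reduces the power of the first primary outcome. Lowering non-response to make room for 76% recovery reduces the power of the non-response row. The relapse analysis includes only recovered children, so its sample also depends on which rate is believed. The SAP further says that outcomes are ranked primary where power is adequate, so these inputs also bear on the ranking.

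**Working it through.** **Inputs.** Analysed n = 360 × 0.85 = 306 per arm; one-sided α = 0.05; equal true rates in the two arms; rates and margins from SAP Table 4. Two scales are shown: the risk difference (RD), in which the Protocol stated its margin, and the log relative risk, the scale of the planned log-binomial analysis.

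**Formulas.** For control rate p and relative margin r:

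- RD: power = Φ( r·p / √(2p(1−p)/n) − 1.645 )
- Log RR: power = Φ( 0.1335 / √(2(1−p)/(p·n)) − 1.645 ), where 0.1335 = −ln 0.875

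**Step 1: reproduce the plan's figure.** At p = 0.76, RD gives Φ(0.0950/0.0345 − 1.645) = Φ(1.11) = 87%, and log RR gives Φ(0.1335/0.0454 − 1.645) = Φ(1.29) = 90%. At the lowest listed MAM recovery, 73%, RD gives 81.5%. The claim of at least 80% is correct at those rates.

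**Step 2: add the MAM inputs.** 76 + 28 = 104% and 76 + 32.2 = 108.2%. With default they are 110.8% and 115.0%.

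**Step 3: keep the non-response rates and find the recovery ceiling.** If default falls wholly inside non-response, the ceiling is 100 − 28 = 72% or 100 − 32.2 = 67.8%. If default is separate, subtracting 6.8 gives 65.2% or 61.0%.

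| MAM recovery | RD, n = 306 | Log RR, n = 306 | RD, n = 360 | Log RR, n = 360 |
|---|---|---|---|---|
| 76% (as sized) | 87% | 90% | 91% | 94% |
| 72% | 80% | 84% | 85% | 89% |
| 67.8% | 73% | 77% | 78.5% | 83% |
| 65.2% | 68% | 73% | 74% | 79% |
| 61.0% | 61% | 66% | 67.5% | 72% |

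**Step 4: keep 76% recovery instead.** MAM non-response is then at most 24%. With its 30% margin, RD power is Φ(0.072/0.0345 − 1.645) = Φ(0.44) = 67% (73% at n = 360). At the listed rates the same row has 75% power at 28% and 82% at 32.2% (n = 306).

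**Step 5: can both rows reach 80%?** On the RD scale, 80% power requires r²p/(1−p) ≥ 2(1.645 + 0.842)²/n = 0.0404 at n = 306, so p ≥ 0.0404/(r² + 0.0404). Recovery (r = 0.125) needs p ≥ 72.1%. Non-response (r = 0.30) needs p ≥ 31.0%. The sum is 103.1%, so they cannot both hold. At n = 360 the thresholds are 68.7% and 27.6%, which sum to about 96%, so this step depends on the stated 15% attrition.

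**Step 6: SAM.** With non-response inside transfer but default separate, 76 + 20.1 + 8.5 = 104.6%. If default and non-response both fall inside transfer, the recovery ceiling is 100 − 20.1 = 79.9%, and 76% is possible. The four rates from source 9 sum to 55.4 + 8.5 + 20.1 + 12.5 = 96.5%. At 55.4% recovery, power is 53% (RD) or 58% (log RR).

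**Step 7: relapse sample.** 306 × 0.76 = 233 and 306 × 0.77 = 236 recovered per arm. At 67.8–72% recovery the number is 207–220, and at 61.0–65.2% it is 187–200. For the Protocol's 30% versus 20% scenario (two-sided 0.05, pooled two-proportion formula), power goes from 70–71% to 65–68% or 61–64%.

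**The case against.** The strongest reply is that Table 4 reports literature prevalence from different studies rather than one planned outcome distribution. The MAM recovery, non-response and default rates have separate sources, whose definitions may differ from the SAP's. The assumed 76% lies inside the listed MAM recovery range of 73–85%, and the stated power reproduces there. This part stands: there is no arithmetic slip in the recovery row. It does not remove the conflict, because footnote 1 makes these values the calculation inputs.

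A second reply is that the SAP never says the categories are exclusive. Non-response can be triggered partway through treatment, and such a child might then default or, on the wording alone, recover. Overlap with default is possible and changes the answer: recovery could be 72%, where power is 80–84%. A reader might infer that MAM recovery power is certainly below 80%, or that recovery cannot exceed 61–65%. The documents do not support either reading, since both need default to be separate. Overlap with recovery is harder to defend, because the SAP sends non-responders to inpatient care and defines unmet recovery at 3 months as non-response.

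A reader might also infer that the SAM inputs are impossible. Full overlap within transfer leaves room for 79.9% recovery, so that does not follow. The 96.5% total from one source suggests separate categories but does not prove it.

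Third, default counts as an outcome, so the 15% attrition may partly count it twice, and n could be nearer 360. That raises every figure, and the joint result in step 5 then no longer holds. At n = 360, 76% recovery still leaves the non-response row at no more than 73%.

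Finally, the SAP describes late enrolment in the past tense, so restated power changes no estimate or decision rule. That limits the consequence to the accuracy of what is stated.

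**Conclusion.** The concern holds for MAM as an inconsistency between inputs. Recovery of 76% and non-response of 28–32.2% cannot both be control rates for the same children, given that a non-responder does not count as recovered. At the stated 306 per arm on the risk-difference scale, no single pair of rates gives both MAM rows 80% power.

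Which row loses power depends on which rate is right, and the documents do not settle that. If the non-response rates are right, recovery power has an upper limit between 61% and 80% by risk difference (66–84% by log relative risk), depending on the non-response rate chosen and on whether default lies inside it. If 76% is right, recovery power stands at 87–90% and the MAM non-response row has at most about 67%.

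For SAM the conflict is conditional on default being separate from transfer. It is still notable that the three failure rates were taken from a source whose own listed recovery, 55.4%, would give 53–58% power.

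**What to change.** For each stratum, state one coherent set of control outcome rates covering recovery, default, transfer, non-response and death. Say which categories may overlap and how a child meeting two of them is counted. Recompute the recovery, default, transfer and non-response rows of SAP Table 4 from that set, along with the recovered-only sample for relapse. State whether defaulters are part of the 15% attrition, since this decides whether 306 or a larger number applies.

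Then replace the general statement of sufficient power, and the entries of at least 80%, with the achieved power over the plausible recovery range. For MAM recovery that range should include 61–76% unless the non-response inputs are revised.

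Enrolment stays unchanged. The cost is the recalculation and some less favourable stated power figures.

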We will conduct a facility-based, individually randomized controlled trial with three arms allocated in a 1:1:1 allocation ratio in 30 health facilities (Centre de Santé et Promotion Sociale [CSPS]) in Burkina Faso. We will randomize 1080 children with MAM and 1080 children with uncomplicated SAM 6-59 months of age to receive treatment with one of the following RUTFs: (1) standard of care, milk- and peanut-based RUTF (control group); (2) SMS-RUTF free of milk and peanuts and high in fiber (intervention 1); or (3) S-RUTF free of milk and peanuts (intervention 2). Children will be enrolled upon presentation to facilities for MAM or uncomplicated SAM treatment. Follow up visits will be weekly during treatment for SAM children and bi-weekly during treatment for MAM children, and monthly for 3 months following discharge from treatment. The primary study outcomes are anthropometric recovery at discharge (a non-inferiority analysis) and relapse to MAM or SAM within the 3 months following recovery (a superiority analysis). We will employ an activity-based micro-costing approach to collect cost data on the direct and indirect medical costs, opportunity costs to caregivers, personnel, and overheads associated with outpatient MAM or SAM treatment. Fecal samples will be collected from children at a subset of facilities (5 facilities, ~60 children per treatment arm), at enrollment (initiation of treatment), discharge from treatment, and 3-months post-discharge. Enrollment is planned to begin in October 2024, and follow up is planned to be completed in August 2025. Final results are planned to be available in December 2025.

Introduction

Globally, 45 million children under the age of five suffer from wasting, a form of acute malnutrition characterized by extreme loss of muscle and fat tissue (1). Acute malnutrition dramatically increases the risk of death; compared to well-nourished children, children with moderate acute malnutrition (MAM) are 3.4 times more likely to die, and this probability increases to a staggering 11.6 times in children with severe acute malnutrition (SAM) (2). Child acute malnutrition is the underlying cause for an estimated annual 875,000 deaths of children under 5 years of age, representing about 12.6% of all deaths in this age group worldwide (3).

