Anthropometric measurements will be taken at treatment initiation and discharge, weekly during the treatment course for SAM children and bi-weekly for MAM children, and monthly during the post-discharge follow-up. The child's weight will be taken using an electronic scale to the nearest 100g. The length will be measured with a measuring board to the nearest 1 mm. MUAC will be measured using a non-stretch tape with 0.1 cm accuracy. All measurements will be taken twice by the study nurses and the average calculated. Weight-for-age, weight-for-length/height, and length/height-for-age z-scores will be calculated using the WHO 2006 growth standards (24).

All children will be tested for malaria upon admission as per national guidelines for wasting treatment (12) through rapid diagnostic test using capillary blood. Capillary blood will be collected from all children via finger prick to measure hemoglobin concentration, at baseline (initiation of treatment) and at discharge.

Costing

We will employ an activity-based costing-ingredients (ABC-I) approach to collect and analyze data on costs incurred in each treatment arm. A societal perspective will be used, which includes all financial and

economic costs regardless of who incurs them; i.e. health system, implementing partners, and patients (25,26). This will include costs and opportunity costs to caregivers. We will have two activities, which are the treatment of MAM and the outpatient treatment of SAM. For these activities, we will assess the cost categories listed in Table 5.

Table 5. Cost categories and their descriptions for costing analyses

Cost category	Description
Direct medical costs	Costs of all equipment, procedures, and consumables (medications and nutrition commodities [RUTFs]) used in the outpatient treatment of SAM or MAM, beginning at admission and ending at discharge
Indirect medical costs	Costs to caregivers incurred due to receiving outpatient SAM treatment, including cost of transportation and any food or lodging costs
Opportunity costs to caregivers	The valuation of the time that caregivers spend on having their child treated for wasting, including time traveling to and spent at OTPs. Missed income will be calculated, and, for caregivers who do not have paid employment outside the home, opportunity costs will be calculated using 60% of national GDP (27,28) and estimated amount of time spent participating in the program.

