## Statistical methods

We will conduct two separate comparisons between (i) the control group and SMS-RUTF, and (ii) between the control group and S-RUTF. All analyses will be done separately by wasting severity status (MAM vs SAM); that is, all analyses will be conducted and presented among MAM children and among SAM children separately. No adjustments for multiple comparisons will be made.

For binary outcomes, we will use log-binomial regression to estimate relative risks (RRs) and 95% confidence intervals (CIs) for the RRs, adjusting for any baseline factors as appropriate (described further below). If the regression model is adjusted, we will present both crude (unadjusted) and adjusted model results. If the models do not converge, we will use Poisson regression models with robust estimation of standard errors (26) and report which model was used. Non-inferiority will be declared if the lower bound of a one-sided 95% CI for the RR lies entirely below the non-inferiority margin of a relative 12.5%. For superiority analyses, we will use a two-sided 95% CI and superiority will be declared if the lower bound of the 95% CI for the relative risk is above 1.0. All analyses will be adjusted for health center to reflect the stratified randomization (27–29).

For continuous outcomes measured at one timepoint, we will use linear regression to estimate differences in that outcome between treatment arms, adjusting for any baseline factors as appropriate and health center (as explained above). Both unadjusted and adjusted model results will be presented.

For any outcome for which non-inferiority is demonstrated, we will then sequentially test for superiority. In these cases, we will report both non-inferiority and superiority results. The superiority analysis will be considered exploratory, as the study power calculations were based on non-inferiority effect size.

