We will conduct one sensitivity analysis. There were children enrolled near the end of the study whose product was switched to standard of care product during their treatment course because the expiration date of the study products occurred during their treatment course. That is, they received the study product to which they were randomized for the majority of their treatment course, and then when the expiration date of that product neared, they received a standard of care product for the remainder of their treatment duration. As these children received both the study and standard of care products, including them in the study arm to which they were randomized represents misclassification and their inclusion could bias the results to the null. If we were to exclude only the children assigned to the expiring product, there is the potential to induce bias by excluding children with long treatment durations or poorer treatment outcomes in one treatment arm, making treatment outcomes spuriously appear worse in this arm. Therefore, we will conduct a sensitivity analysis excluding all children in all treatment arms who received product on or after the date on which this switch was made.

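### SAP makes six Protocol-secondary outcome groups primary on a power criterion that its Table 4 does not meet for length of stay or MAM weight gain: 72 unadjusted primary tests against 8

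*SAP*

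**What the plan says.** The Protocol abstract states: "The primary study outcomes are anthropometric recovery at discharge (a non-inferiority analysis) and relapse to MAM or SAM within the 3 months following recovery". Protocol Table 3 agrees. It lists length of stay, weight gain, anthropometry at discharge and at 3 months, and hemoglobin at both times as secondary.

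The SAP's section on sample size and power for the main trial still calls recovery and relapse the key objectives, and the SAP objectives list only those two. The same sentence then says "we consider as primary outcomes any outcome for which we have adequate power for clinically or policy meaningful effect sizes". SAP Tables 1 and 4 accordingly rank the six groups as primary.

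Table 4 presents its margins as having at least 80% power for non-inferiority, and its effect sizes as detectable at 80% power for superiority. The MAM weight-gain entry reads "MAM: 0.14 kg; 12.5% relative margin".

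Under Statistical methods the SAP says "We will conduct two separate comparisons between (i) the control group and SMS-RUTF, and (ii) between the control group and S-RUTF", runs every analysis separately in MAM and SAM children, and adds "No adjustments for multiple comparisons will be made". The same section reports, in the past tense, that "There were children enrolled near the end of the study whose product was switched to standard of care product during their treatment course". The Protocol's statistical section had said that the SAP would be final before enrolment began.

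**The concern.** Primary status should follow from the question the trial was set up to answer. Here it follows from power, so the primary family grows with every outcome that has a large enough margin or a small enough SD. With 18 primary variables, two products and two strata, and no rule for reading mixed results, a favourable primary finding somewhere says little. The two results that matter for adopting these products, recovery and relapse, lose their standing.

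The change departs from the Protocol and appears in a SAP version written after late-enrolment events. If the power figures that justify the promotion are wrong for some of the promoted outcomes, the rule fails on its own terms. A failure to show non-inferiority on those outcomes would then be hard to interpret.

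**Working it through.** **1. Number of primary tests**

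SAP Table 1: recovery 1 + relapse 1 + length of stay 1 + weight gain 1 + anthropometry at discharge 6 + anthropometry at 3 months 6 + hemoglobin at discharge 1 + hemoglobin at 3 months 1 = 18 variables.

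- SAP: 18 × 2 comparisons × 2 strata = 72 tests. Of these, 10 × 4 = 40 are non-inferiority and 8 × 4 = 32 are superiority.
- Protocol: 2 × 2 × 2 = 8 tests.

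If neither product had any effect on any superiority outcome, the expected number of false favourable results is 32 × 0.025 = 0.8, against 4 × 0.025 = 0.1 under the Protocol. These expectations do not need independence between outcomes.

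**2. Inputs for power**

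- One-sided α = 0.05 for non-inferiority; 360 per arm per stratum; 15% attrition, so 306 analysed (SAP sample-size section; Protocol Table 4).
- Recovered children: 236 per arm (Protocol Table 4, 77% of 306). The SAP's 76% gives 233, which changes little.
- Means, SDs and margins: SAP Table 4.

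**3. Formula, and a check on figures the plan gives**

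Power = Φ(margin / SE − 1.645), with a true difference of zero. For means, SE = SD × √(2/n).

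- Protocol recovery row, 77% with a 10-point margin, n = 306: SE = √(2 × 0.77 × 0.23 / 306) = 0.0340; power 90.2%. The Protocol states 90.0%.
- Hemoglobin at discharge, n = 306: MAM (2.7 g/L, SD 13) 82.2%; SAM (2.2 g/L, SD 11.2) 78.4%.
- Hemoglobin at 3 months (2.9 g/L, two-sided 0.05): MAM 78.8% at n = 306; SAM 89.3% at n = 306 or 80.3% at n = 236.

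So the method reproduces the recovery figure and comes close on the hemoglobin rows.

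**4. Length of stay, defined among recovered children**

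| Row | n per arm | SE (days) | Margin / SE | Power |
|---|---|---|---|---|
| MAM, 4.9 days, SD 50.4 | 236 | 4.64 | 1.056 | 27.8% |
| same | 306 | 4.07 | 1.203 | 32.9% |
| same | 360 | 3.76 | 1.304 | 36.7% |
| SAM, 8 days, SD 41 | 236 | 3.77 | 2.120 | 68.3% |
| same | 306 | 3.31 | 2.414 | 77.9% |
| same | 360 | 3.06 | 2.618 | 83.5% |
| SAM, 7 days, SD 41 | 236 | 3.77 | 1.855 | 58.3% |

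The 7-day line is included because 12.5% of 56 is 7 days; 8 days is 8/56 = 14.3%.

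The MAM SD also cannot occur in this trial. For a stay between 0 and 84 days with mean 36.4, the largest possible SD is √(36.4 × (84 − 36.4)) = 41.6 days. With a 91-day limit it is √(36.4 × 54.6) = 44.6 days, still below 50.4.

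**5. Weight gain, n = 306**

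- MAM: 12.5% × 4.1 = 0.5125 g/kg/day; SE = 3.0 × √(2/306) = 0.2425; ratio 2.113; power 68.0%. With all 360 it is 74.1%. The printed 0.14 kg is in a different unit and cannot be checked.
- SAM: 0.91 g/kg/day, SE = 4.7 × √(2/306) = 0.380; ratio 2.395; power 77.3%.

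**6. Rows that cannot be checked, and one label**

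Table 4 gives no SDs for anthropometry, so those margins cannot be tested directly. The SAM hemoglobin margin at discharge, 2.2 g/L, is 2.2/108.6 = 2.0%, not the 2.5% printed.

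**The case against.** The SAP does keep recovery and relapse as its key objectives, and that limits the harm if the reporting follows it. It does not undo the ranking in Tables 1 and 4.

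A reader might infer that the power claim fails across all six groups. The documents do not support that. The hemoglobin rows roughly reproduce, anthropometry has no stated SDs, and SAM weight gain is only about 3 points short. Its 0.91 g/kg/day is 12.5% of 7.28, which lies between the two age-specific means of 3 and 8.6, so it may come from an age-weighted mean that is not shown.

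The 28% for MAM length of stay rests on an SD that this trial cannot produce, so it is not a forecast of actual power. A smaller SD could rescue the row: 4.9 days has 80% power at an SD of about 21 days (n = 236) or 24 days (n = 306). That stands. But the SAP states no such SD, and at the one it states the claim fails at every n. The SAM SD of 41 days should not be called impossible: the maximum at mean 56 is √(56 × 28) = 39.6 days for an 84-day cap but √(56 × 35) = 44.3 days for 91 days, and the definition of non-response speaks of 3 months.

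A reader might also infer that outcomes were promoted after seeing results by arm. Nothing supports this. The allocation codes are withheld until analysis is complete, no interim analysis is planned, and the monitoring board receives only blinded descriptive data. The past tense shows that this version is late, not that selection was driven by data.

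**Conclusion.** Wrong as written, on two counts.

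First, the power-based rule turns 2 primary variables into 18, and 8 primary tests into 72, without adjustment and against Protocol Table 3. This needs no assumption beyond counting the six anthropometric measures separately, as SAP Tables 1 and 4 list them.

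Second, Table 4's 80% is not delivered at its stated inputs for length of stay (MAM 28% at n = 236 and 37% even at n = 360; SAM 68% at n = 236) or for MAM weight gain (68% at n = 306). SAM weight gain is slightly short at 77%. SAM length of stay reaches 80% only if all 360 enrolled children are counted, which contradicts its restriction to recovered children. These figures assume a true difference of zero, a normal approximation and the SAP's own SDs.

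The conclusion does not extend to hemoglobin, and for anthropometry it is untested. Confidence is high on the ranking and on MAM length of stay. For the other rows it depends on which n and SD the authors used, which the SAP should state.

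**What to change.** 1. Delete the promotion sentence in the SAP's sample-size section. Keep recovery and relapse as the only primary outcomes, as in Protocol Table 3, and rank the other six groups secondary in SAP Tables 1 and 4.
2. In the length-of-stay and weight-gain rows, state the SD and n used. For length of stay, use recovered children and an SD that is possible under the treatment cap. Give the MAM weight-gain margin in g/kg/day and show the mean behind the SAM margin.
3. Correct the percentage labels: 8 days is not 12.5% of 56, and 2.2 g/L is not 2.5% of 108.6.
4. Restate the achieved power for each corrected row. Do not widen a margin to reach 80%; a margin needs a clinical or policy reason.

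The cost is table and text edits in the SAP. No data collection changes and every outcome is still reported. The downside is that fewer outcomes can be headlined as primary.
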